^b The Discontinuation (D/C) Visit is to be performed only if the subject does not complete the 64 week treatment. The D/C visit should be performed as soon as possible once the subject has prematurely stopped the study medication.

- c The post-treatment follow-up visit is to be scheduled at least 21 days (but no more than 45 days) after the last dose of MK-8962, and at least 7 days after the last dose of hCG (whether subject completed the trial or discontinued from the trial prematurely). Follow-up blood samples will be collected for assessment of anti-MK-8962 antibodies and PK for MK-8962 concentration. AEs and concomitant medication will also be assessed. For subjects wishing to continue on post-trial gonadotropin treatment, such treatment should not be started until after blood sample collection at this visit. For subjects who prematurely discontinue study medication, after the post-treatment follow-up visit, subjects who do not withdraw consent should: (1) return to the clinic for key visits (V9/Week 12, V12/Week 36 and/or V15/Week 64 as applicable) to have the following procedures performed: focus physical examination, vital signs, weight and height, Tanner staging, testicular ultrasound, laboratory assessment of endocrine parameters, and safety parameters (chemistry panel and hematology), and collection of concomitant medications and adverse events. Subjects discontinued from the treatment due to the presence of neutralizing ADAs will also have serum samples collected for ADA testing. Subjects who are unable or unwilling to return to the clinic at key visits will be contacted by phone to obtain adverse events and concomitant medications. (2) be contacted by phone in a timeframe similar to their original study visit schedule at visits that are not key visits, i.e., at V10, V11, V13, V14, up until the subject has reached Week 64 after V2, to assess for serious adverse events and concomitant medications. (3) Subjects discontinued from the treatment due to the presence of neutralizing antibodies may continue to be followed until the ADA result becomes negative or until clinically stable for up to 12 months after treatment discontinuation. Refer to Section 7.1.5.3 for further details.
- d For visits not involving PK sampling, a scheduling window of \pm 7 days is allowed.
- e No further injection of MK-8962 or hCG is administered at the Week 64 visit.

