- o At Visit 1/Screening, testicular ultrasound images will be read locally by the investigator (if qualified) or a local radiologist with appropriate training and expertise in reading testicular ultrasound. This local reader will calculate testicular volume to evaluate Inclusion Criterion #5, and evaluate the ultrasound for any presence of local pathology that would exclude the subject from participating (see Section 5.1.3 Subject Exclusion Criteria). In addition, all testicular ultrasound images will be sent to a central imaging vendor, and will be read in a masked manner after the subject completes participation in the study to assess study endpoints (i.e., testicular volume and sonographic pattern).
- p If testicular ultrasound or endocrine parameters is not able to be completed at study completion (V15) or on the day of D/C, the site should make an effort to schedule a visit within 4 weeks from the last dose of MK-8962 to perform these procedures. This visit can be combined with the post-treatment follow-up visit if it is scheduled at 21-28 days after the last dose of MK-8962. Testicular ultrasound does not need to be performed at D/C if this visit is \leq 6 weeks from the last scheduled testicular ultrasound measurement.

- ^q The investigator will use clinical assessment to assign the Tanner Stage for pubic hair and Tanner Stage for genital growth (e.g., penile length and scrotum development) separately, and perform a testicular ultrasound to measure testicular parameters as according to the procedures outlined in the Site Imaging Manual provided to the investigator site. The Tanner Stage for testicular volume will not be assessed clinically by the investigator and will be completed by the central imaging vendor according to the method described in the Independent Review Charter for imaging.
- ^r These blood sample collections should be performed prior to the injection(s) of MK-8962 or hCG, if there is any injection(s) scheduled for that day. Leftover main study serum will be stored at the end of the study for future biomedical research if the subject consents to future biomedical research.

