7.1.5.3 Post-Treatment

- Post-treatment Follow-up Visits for Subjects Who Complete the Study or Who Discontinue Treatment but Do Not Withdraw Consent***

The last dose of MK-8962 is scheduled to be self-administered or administered by the subject's legal guardian (or someone designated by the legal guardian who has been appropriately trained) on Week 62. The subject will continue twice-weekly hCG injections with the last two doses administered in Week 64. A post-treatment follow-up visit is to be scheduled at least 21 days (but no more than 45 days) after the last dose of MK-8962, and at least 7 days after the last dose of hCG, whether the subject completed the trial or discontinued from the trial treatment prematurely. Follow-up blood samples will be

collected for assessment of anti-MK-8962 antibodies and endocrine parameters. AEs and concomitant medication will also be assessed. For subjects wishing to continue on post-trial gonadotropin treatment, such treatment should not be started until after blood sample collection at this visit.

For subjects who discontinue treatment but do not withdraw consent, after the discontinuation visits and post-treatment follow-up visit, they should:

1. Return to the clinic for key visits (V9/Week 12, V12/Week 36 and/or V15/Week 64 as applicable) to have the following procedures performed: focus physical examination, vital signs, weight and height, Tanner staging, testicular ultrasound, laboratory assessment of endocrine parameters, and safety parameters (chemistry panel and hematology), and collection of concomitant medications and adverse events. Subjects who discontinued treatment due to presence of ADA will also have serum samples collected for ADA testing at these visits. Subjects who are unable or unwilling to return to the clinic at key visits will be contacted by phone to obtain adverse events and concomitant medications.
2. Be contacted by phone in a timeframe similar to their original study visit schedule at visits that are not key visits, i.e., at V10, V11, V13, V14, up until the subject has reached the Week 64 visit. The purpose of these telephone contacts will be to assess for serious adverse events that occurred and to collect the subject's concomitant medications. The date of the telephone contact should be recorded and any serious adverse events that have occurred and concomitant medications that were used should be recorded in the eCRF.

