8.4.1 Efficacy/Immunogenicity/Pharmacokinetics Endpoints

Primary Efficacy Endpoint

The primary efficacy endpoint for this trial is the Change from Baseline (Day 1) to Week 64 in log-transformed testicular volume (measured as the sum of volumes of left and right testes by ultrasound).

Secondary Efficacy Endpoint

- Change from baseline in serum inhibin B concentrations at Week 64;
- Growth velocity at Week 36 and Week 64;
- Tanner Stage of pubertal development at Weeks 12, 36 and 64.
- Characterization of MK-8962 pharmacokinetics (based on serum MK-8962 concentrations) through 64 weeks of treatment.

- Characterization of testicular sonographic pattern reflecting pubertal development through 64 weeks of treatment;
- Changes from baseline in endocrine parameters (LH, calculated free testosterone, Total T, E2, SHBG, and AMH at Weeks 12, 36 and 64;

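### A Week 64 hormone panel made up at the follow-up visit falls 10-18 days after the last hCG dose for an on-schedule completer, and no analysis rule keeps it out of the Week 64 results

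*Combined protocol and SAP*

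**What the plan says.** Footnote p of the flow chart (Section 6.0) applies when an ultrasound or an endocrine panel could not be done at V15 or on the day of discontinuation. The site should try to "schedule a visit within 4 weeks from the last dose of MK-8962 to perform these procedures". The footnote then adds: "This visit can be combined with the post-treatment follow-up visit if it is scheduled at 21-28 days after the last dose of MK-8962". The flow chart attaches it to the ultrasound row and to both endocrine rows. It does not mention time since hCG.

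Footnote c places the follow-up visit "at least 21 days (but no more than 45 days) after the last dose of MK-8962". A second condition in the same footnote concerns the other drug: "and at least 7 days after the last dose of hCG". For boys who will go on to gonadotropin treatment after the trial, "such treatment should not be started until after blood sample collection at this visit". A panel drawn at that visit is therefore taken with hCG stopped and nothing yet in its place.

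Section 8.4.1 lists as a secondary endpoint "Changes from baseline in endocrine parameters (LH, calculated free testosterone, Total T, E2, SHBG, and AMH at Weeks 12, 36 and 64". Section 8.6.1.2 summarises hormones by assessment and by treatment phase, with no visit window and no rule on time since the last injection. The only recency limit in the analysis is in the FAS definition (Section 8.5.1). It allows up to 4 weeks since MK-8962 and does not mention hCG.

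The documents also differ on what is drawn at follow-up. Footnote c says: "Follow-up blood samples will be collected for assessment of anti-MK-8962 antibodies and PK for MK-8962 concentration". Section 7.1.5.3 says that samples are "collected for assessment of anti-MK-8962 antibodies and endocrine parameters", without condition. The flow chart shows the endocrine rows at follow-up only as a bracketed, conditional entry. Section 12.4 includes the post-treatment visit in a full endocrine column.

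**The concern.** Sharing one make-up rule treats two different measurements alike. Testosterone and estradiol are the quantities that hCG is titrated to control (Section 5.2.1.2), and Section 4.1.1 describes hCG as the agent that raises testosterone production. Their values depend on how recently hCG was injected, yet the rule counts time from the other drug.

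At stake is the meaning of the Week 64 hormone results, which are there to describe the response at the end of combined treatment. Boys enter with total testosterone below 8.3 nmol/L. A value taken after hCG has stopped would be expected to move back towards that level, so the error runs in one direction. With about 10 completers, one or two such values are enough to shift a summary.

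**Working it through.** **Inputs.** Last MK-8962 dose on Day 435 (Table 2, flow chart). V15 on Day 449 (flow chart). No injection of either drug at V15 (footnote e). Example hCG weekdays from Table 3. About 10 completers (Section 8.9.1).

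**Reproducing the plan's own timing.** The flow chart puts the follow-up visit 7 days after V15, with a window of +24 days.
- Earliest: 435 + 21 = Day 456, and 456 - 449 = 7.
- Latest: 435 + 45 = Day 480, and 480 - 456 = 24.

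Both figures match. The combined make-up visit covers the part 21-28 days after MK-8962: 435 + 21 = Day 456 to 435 + 28 = Day 463.

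**Last hCG dose before V15.** Days 435, 442 and 449 fall on the same weekday as the MK-8962 injection. In schedules A-C the second weekly hCG dose comes 3 days after that weekday, so the last dose is 442 + 3 = Day 445. In D-E it comes 4 days after, so the last dose is 442 + 4 = Day 446.

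**Days since the last dose.**

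| Sample | Since MK-8962 | Since hCG, A-C | Since hCG, D-E |
|---|---|---|---|
| V15, Day 449 | 14 | 449 - 445 = 4 | 449 - 446 = 3 |
| Combined visit, Day 456 | 21 | 456 - 445 = 11 | 456 - 446 = 10 |
| Combined visit, Day 463 | 28 | 463 - 445 = 18 | 463 - 446 = 17 |

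The hCG gap is 3-4 days at V15 and 10-18 days at the combined visit. For an on-schedule completer the 7-day minimum in footnote c is therefore not the binding limit. Table 3 is illustrative and other schedules are allowed. Even a last dose on Day 448, the day before V15, would give 456 - 448 = 8 to 463 - 448 = 15 days.

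**Size, as illustration only.** The documents give no rate at which testosterone or estradiol falls after hCG stops, so the fall has to be assumed. If k of 10 Week 64 values drop to a fraction f of their on-treatment level, the geometric mean is multiplied by f^(k/10). With baseline unchanged, the geometric mean ratio to baseline moves by the same factor.

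| Assumed f | k = 1 | k = 2 |
|---|---|---|
| 0.75 | 0.97 | 0.94 |
| 0.50 | 0.93 | 0.87 |
| 0.25 | 0.87 | 0.76 |

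The documents give no expected number of missed V15 panels, so k is also an assumption.

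**The case against.** The strongest reply is that the substitution is inferred. No passage says that a make-up panel will be labelled Week 64. Hormones are also to be summarised by treatment phase, and Section 8.0 leaves room for a supplemental SAP. That is correct: a reader might infer a plan to pool off-treatment values, and the documents do not show one. What they show is a rule that allows the draw as a replacement for a V15 procedure, and an analysis section with nothing to separate it.

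The route is also optional and probably uncommon. It applies only when the panel could not be done at V15 or at discontinuation, and an earlier make-up visit is allowed. The endpoints are secondary, in an estimation study that tests no hypothesis. All of this stands and limits the weight of the point.

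Three stronger readings are tempting and are not supported.
- **Every boy at some sites.** Because Section 7.1.5.3 lists endocrine sampling at follow-up without condition, a reader might infer that some sites would have off-treatment Week 64 values throughout. Those sites would still draw the V15 panel, and an additional later sample does not replace an existing value.
- **Inhibin B and MK-8962.** A reader might object equally to a draw at 21-28 days after MK-8962 instead of 14. That tolerance agrees with the 4-week limit in the FAS definition and looks deliberate. The gap that no rule addresses is hCG.
- **A definite size.** A decay curve for hCG, or a fall in testosterone in nmol/L, would need figures that the documents do not contain.

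Affected samples can be identified afterwards, since the diary records injection times and serum hCG is part of the same panel. That makes the remedy easy, but it does not supply the missing rule.

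**Conclusion.** The point holds in a limited form. For total testosterone, estradiol and calculated free testosterone, footnote p permits a make-up sample 10-18 days after the last hCG dose where V15 would have been at 3-4 days, and the analysis plan does not keep it out of the Week 64 change from baseline. Any resulting bias would understate the on-treatment response. Its size is unknown; the factor of 0.93 rests on an assumed halving in one boy out of 10.

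The 10-18 days assume an on-schedule completer following one of the Table 3 examples. The direction rests on the protocol's own account that hCG drives testosterone production. The hormone argument does not reach the primary endpoint, and it gives no reason to change the ultrasound make-up rule.

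The disagreement over follow-up blood sampling is real but separate. It is a documentation inconsistency and not evidence of bias in the Week 64 results.

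**What to change.** In Section 8.6.1.2, pre-specify a numeric maximum number of days since the last hCG dose, taken from diary times, for a hormone sample to count as Week 64. Report samples outside it as a separate post-treatment time point, state how many there are, and show the Week 64 summary with and without them. Add a pointer to this rule in footnote p.

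The number is for the sponsor to choose. On the Table 3 schedules, any limit of at least 4 and below 7 days keeps an on-schedule V15 draw and excludes every draw at a follow-up visit that respects the 7-day minimum. A limit of 6 days, for example, would still accept a make-up draw until Day 445 + 6 = 451 (schedules A-C) or 446 + 6 = 452 (D-E).

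Separately, reconcile the flow chart, footnote c, Section 7.1.5.3 and Section 12.4 on whether endocrine parameters are drawn at follow-up routinely or only as a make-up.

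The cost is a few sentences of protocol and SAP text, using injection times that are already collected. The analysis rule needs no new visit or sample. The downside is that a few Week 64 hormone values may drop out of the main summary, which matters with about 10 completers and is the reason to show both versions.

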7.0 TRIAL PROCEDURES

7.1 Trial Procedures

The Trial Flow Chart - Section 6.0 summarizes the trial procedures to be performed at each visit. Individual trial procedures are described in detail below. It may be necessary to perform these procedures at unscheduled time points if deemed clinically necessary by the investigator.

Furthermore, additional evaluations/testing may be deemed necessary by the investigator and or the Sponsor for reasons related to subject safety. In some cases, such evaluation/testing may be potentially sensitive in nature (e.g., HIV, Hepatitis C, etc.), and thus local regulations may require that additional informed consent and/or assent (if applicable) be obtained from the subject. In these cases, such evaluations/testing will be performed in accordance with those regulations.

7.1.1 Administrative Procedures

7.1.1.1 Informed Consent/Assent

The investigator or qualified designee must obtain documented consent/assent (if applicable) from each potential subject or each subject's legally acceptable representative prior to participating in a clinical trial or Future Biomedical Research.

7.1.1.1.1 General Informed Consent/Assent

Consent/assent must be documented by the subject's dated signature or by the subject's legally acceptable representative's dated signature on a consent/assent form along with the dated signature of the person conducting the consent discussion.

A copy of the signed and dated consent/assent form should be given to the subject before participation in the trial.

The initial informed consent/assent form, any subsequent revised written informed consent/assent form and any written information provided to the subject must receive the IRB/ERC's approval/favorable opinion in advance of use. The subject or his/her legally acceptable representative should be informed in a timely manner if new information becomes available that may be relevant to the subject's willingness to continue participation in the trial. The communication of this information will be provided and documented via a revised consent/assent form or addendum to the original consent/assent form that captures the subject's dated signature or by the subject's legally acceptable representative's dated signature.

Specifics about a trial and the trial population will be added to the consent/assent form template at the protocol level.

The informed consent will adhere to IRB/ERC requirements, applicable laws and regulations and Sponsor requirements. The assent, as applicable, will adhere to IRB/ERC requirements, applicable laws and regulations and Sponsor requirements.

7.1.1.1.2 Consent/Accent and Collection of Specimens for Future Biomedical Research

The investigator or qualified designee will explain the Future Biomedical Research consent/assent to the subject, answer all of his/her questions, and obtain written informed consent/assent before performing any procedure related to the Future Biomedical Research sub-trial. A copy of the informed consent/assent will be given to the subject.

7.1.1.2 Inclusion/Exclusion Criteria

All inclusion and exclusion criteria will be reviewed by the investigator or qualified designee to ensure that the subject qualifies for the trial.

7.1.1.3 Subject Identification Card

All subjects will be given a Subject Identification Card identifying them as participants in a research trial. The card will contain trial site contact information (including direct telephone numbers) to be utilized in the event of an emergency. The investigator or qualified designee will provide the subject with a Subject Identification Card immediately after the subject provides written informed consent/assent.

The subject identification card also contains contact information for the emergency unblinding call center so that a health care provider can obtain information about trial medication/vaccination in emergency situations where the investigator is not available.

7.1.1.4 Medical History

A medical history will be obtained by the investigator or qualified designee at screening. Include any medical history related to andrologic history on this form (e.g., hypogonadotropic hypogonadism; prior genital, pelvic or inguinal surgery; infections such as epididymitis or orchitis; presence of varicocele, including grade; etc).

7.1.1.5 Prior and Concomitant Medications Review

7.1.1.5.1 Prior Medications

The investigator or qualified designee will review prior medication use (i.e., used within 6 months of starting the trial) by the subject. Additionally, the use of any medications noted in [Table 1](#) should be reviewed to determine that the required washout periods have been met.

7.1.1.5.2 Concomitant Medications

The investigator or qualified designee will record medication, if any, taken by the subject during the trial.

7.1.1.6 Assignment of Screening Number

All consented subjects will be given a unique screening number that will be used to identify the subject for all procedures that occur prior to randomization or treatment allocation. Each subject will be assigned only one screening number. Screening numbers must not be re-used for different subjects.

Any subject who is screened multiple times will retain the original screening number assigned at the initial screening visit.

Specific details on the screening visit requirements (screening/rescreening) are provided in Section 7.1.5.1.

7.1.1.7 Assignment of Treatment/Randomization Number

All eligible subjects will be allocated, by non-random assignment, and will receive a treatment/randomization number. The treatment/randomization number identifies the subject for all procedures occurring after treatment allocation/randomization. Once a treatment/randomization number is assigned to a subject, it can never be re-assigned to another subject.

A single subject cannot be assigned more than 1 treatment/randomization number.

7.1.1.8 Trial Compliance (Medication)

A paper diary will be used to record the time and dosage of MK-8962 and hCG administration. The first paper diary will be dispensed at Visit 2, and the site staff should train subjects on how to complete the paper diary. At subsequent visits specified in the Trial Flow Chart (Section 6.0), the site will collect and review the diary dispensed at the previous visit, and dispense a new diary to the subject. The information as recorded on the diary by the subject serves as the source for data entry by the site on the medication eCRF.

At all protocol-specified visits, the investigator or qualified designee is to record whether treatment has been taken per protocol in the preceding interval. If not, the date(s) and reason for each dosing noncompliance must be recorded.

Interruptions from the protocol specified treatment (in the case when the subject misses more than 2 doses of MK-8962 or more than 2 consecutive doses of hCG) require consultation between the investigator and the Sponsor and written documentation of the collaborative decision on subject management.

Administration of the first 3 doses of MK-8962 and the first dose of hCG will be witnessed by the investigator and/or trial staff.

